 - This hypothesis will be tested using a repeated measures analysis of covariance where the pre-HUT CBFv will be used as the covariate and the adjusted post-HUT CBFv scores will serve as the dependent variable. In addition, the covariate adjusted point estimate and 95% confidence interval of the differences between drug conditions (droxidopa vs. placebo) will provide the first reported estimate describing the effect of droxidopa on the CBFv response to HUT.
- **Hypothesis 2.4** – Plasma renin and serum aldosterone concentrations will be reduced and plasma norepinephrine concentrations will be increased during HUT following administration of droxidopa compared to placebo.
 - These hypotheses will be tested using a repeated measures analysis of covariance where the pre-HUT concentrations will be used as the covariate and the adjusted post-HUT concentrations will serve as the dependent variable. In addition, the covariate adjusted point estimate and 95% confidence interval of the differences between drug conditions (droxidopa vs. placebo) will provide the first

reported estimate describing the effect of droxidopa on these vasoactive substances in response to HUT.

Safety Monitoring:

As is stated in the consent forms there is a risk of increased systemic blood pressure following administration of droxidopa.

Laboratory Monitoring: During the laboratory observation heart rate and blood pressure will be closely monitored at 15 minute intervals and action will be taken if blood pressure is elevated above 140/90 mmHg for more than 30 minutes. The action plan to lower blood pressure in the laboratory is as follows:

1. Loosening of clothing or braces
2. Re-positioning the participant in his/her wheelchair
3. Emptying of the bladder/catheter bag

If these measures prove unsuccessful in lowering blood pressure the study physician will be alerted and brought to the laboratory for further subject monitoring and administration of an anti-hypertensive agent if deemed necessary. The medication of choice will be sub-lingual nitroglycerin.

The study clinician, [name] will monitor and review all blood pressure recordings during each laboratory visit in both Study 1 and 2. Although he will not be in the laboratory for the duration of testing, his office is across the hall and he is readily accessible if needed.

Testing will be scheduled when [name] is in the office only.

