IND number or other status (submit validation or correspondence): **137213**

If there is no IND number, is there an FDA exemption? (If yes, please submit FDA correspondence.)? **See attached FDA IND letter.**

YES	X	NO	
-----	---	----	--

d. Will investigational devices be used:

No.

Is there an IDE issued by the FDA? **N/A**

YES		NO	
-----	--	----	--

IDE number or other status (submit validation or correspondence):

Is there an abbreviated IDE?

YES		NO	
-----	--	----	--

If there is no IDE number, is there an FDA exemption? (If yes, please submit correspondence with FDA.)?

YES		NO	
-----	--	----	--

How would you determine the risk-benefit analysis for investigational devices?

e. Risks for Investigational Drugs/Device:

For investigational drugs, what are the possible risks associated with the study drug relative to possible interactions with medications likely to be used by subjects? **Following droxidopa, administration BP may elevate above the normal range (>140/90 mmHg). In addition, symptoms of autonomic dysreflexia (AD) may become frequent or worsen while taking the study medication. Clinical staff will assist the subject to an upright seated position, loosen any tight clothing or braces that the subject is wearing and may check and empty your bladder and bowel. If BP remains high for more than 30 minutes the subject will be provided with a medication to lower their pressure. The medication of choice will be a nitropaste (Nitroglycerin Ointment, 2%) that will be placed one inch on the subjects forehead.**

Droxidopa risks ($\leq 8\%$ likely) include: slow or fast heartbeat, pounding in the ears, low back or side pain, and nervousness.

Since this research may have unknown effects on an unborn child and should not be done during pregnancy, it is necessary for a pregnancy test to be done first. To your knowledge you are not pregnant at the present time. You also agree to avoid becoming pregnant (use contraceptives, take precautions against becoming pregnant, etc.) during this study.

As with any research, there may be unforeseen risks and discomforts. A medical doctor associated with the study will be available to treat any medical emergency that may develop.

What will your approach be to such risks? **Study personnel and clinical staff will monitor BP daily during the study participation period.**

Will such subjects be excluded from the study? **No.**

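### The two documents give conflicting rescue instructions for BP above 140/90 mmHg: formulation and route, the step that 30 minutes triggers, and the decision step all differ

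*Protocol*

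**What the plan says.** **Protocol, Safety Monitoring, Laboratory Monitoring.** The starting condition is that "action will be taken if blood pressure is elevated above 140/90 mmHg for more than 30 minutes". The action plan then lists three non-drug measures: loosening clothing or braces, repositioning in the wheelchair, and emptying the bladder or catheter bag. The next step reads: "If these measures prove unsuccessful in lowering blood pressure the study physician will be alerted and brought to the laboratory". The physician's role includes "administration of an anti-hypertensive agent if deemed necessary". On the product: "The medication of choice will be sub-lingual nitroglycerin".

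**Combined protocol and SAP, item 15e (Risks for Investigational Drugs/Device).** The event is described as follows: "administration BP may elevate above the normal range (>140/90 mmHg" (the bracket closes there). The first step is: "Clinical staff will assist the subject to an upright seated position, loosen any tight clothing or braces that the subject is wearing"; the bladder and bowel may also be checked and emptied. Then: "If BP remains high for more than 30 minutes the subject will be provided with a medication to lower their pressure". On the product: "The medication of choice will be a nitropaste (Nitroglycerin Ointment, 2" per cent), applied to the forehead.

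Both passages are current text. Neither document says which takes precedence, and the combined document is an application that requires a research protocol to be submitted with it, so the two are meant to be read together.

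**The concern.** Each document names a single preferred product for the same event, and the products differ in formulation and route. The Protocol (Study Procedures) promises identical procedures at JJPVAMC and ISMMS. The combined document covers those two sites and adds KF. A staff member facing a sustained elevation would therefore act differently depending on which document is to hand.

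The main stake is participant safety. The Protocol (Significance) describes autonomic dysreflexia in this population as potentially life threatening, the combined document rates the study as greater than minimal risk, and this instruction is the laboratory safeguard against sustained high pressure.

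The second stake is narrower. In Study 1, seated readings continue at 15-minute intervals for 4 hours, and neither document says how readings taken after a rescue drug are handled. Whether and when a drug is given could therefore reach an endpoint in some participants.

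**Working it through.** The plan has no figure to reproduce here. The check sets the passages side by side and then asks where a rescue drug could meet an endpoint.

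**1. Side by side**

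| Element | Protocol, Laboratory Monitoring | Combined document, item 15e | Agree? |
|---|---|---|---|
| BP level | above 140/90 mmHg | above 140/90 mmHg | yes |
| Duration named | more than 30 minutes | more than 30 minutes | yes |
| Non-drug measures before a drug | yes | yes | yes |
| Active substance | nitroglycerin | nitroglycerin | yes |
| What the 30 minutes starts | non-drug measures | the drug | no |
| Wait before non-drug measures | more than 30 minutes | none stated | no |
| Decision to give the drug | study physician's judgement, no time set | given; no physician decision stated | no |
| Formulation and route | sub-lingual | 2% ointment on the forehead | no |

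**2. Can one course of action satisfy both?**

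- *Timing.* Sometimes. If non-drug measures start after more than 30 minutes, fail, and a drug follows, pressure has been high for more than 30 minutes under either text.
- *Decision.* Only if the physician decides to give a drug. If the physician withholds it, the Protocol is satisfied and the combined document, read literally, is not.
- *Product and route.* No. Each document names one preferred product, and they are not the same.

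**3. Where rescue could meet an endpoint (Study 1)**

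The normotensive response (Efficacy #1) is the average SBP at 60-120 minutes after the dose. With 15-minute readings that is five values: 60, 75, 90, 105 and 120 minutes. A drug can affect this average only if it is given before 120 minutes. Since both texts require more than 30 minutes of elevation before any drug, the elevation must begin before 120 − 30 = 90 minutes.

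A hypothetical case, with values assumed and not taken from the documents: SBP is 150 mmHg from 45 minutes.

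- Drug given after the 90-minute reading, SBP then 115: (150 + 150 + 150 + 115 + 115) / 5 = 680 / 5 = 136 mmHg, inside the normotensive range for both sexes (upper limit 139).
- No drug, SBP stays at 150: the average is 150 mmHg, outside the range.

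How far SBP must fall for this to happen:

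- Two readings affected: (3 × 150 + 2x) / 5 ≤ 139 gives x ≤ (695 − 450) / 2 = 122.5 mmHg.
- One reading affected: (4 × 150 + x) / 5 ≤ 139 gives x ≤ 695 − 600 = 95 mmHg.

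So the classification can change, but only with an early elevation and a substantial fall inside the window. The documents give no onset or effect data for either formulation, so they cannot show that the two products would give different averages.

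The hypertensive response (Safety #1) is a sustained elevation of at least 30 consecutive minutes at 140/100 mmHg. In the example its systolic criterion is met at 45 + 30 = 75 minutes, before any drug. A later drug does not undo it.

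**The case against.** The strongest reply is that the conflict is small. Both products are nitroglycerin, both texts use the same level and duration, and both put non-drug measures first. Item 15e answers a risk question on a review-board form, partly in consent-form language. Its silence on who decides need not remove the physician, and it says a study doctor will be available for emergencies.

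Most of that stands, and it limits the point. It does not explain why two formulations are each named as the preferred one, and no other text resolves that.

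Several stronger readings are tempting and are not supported:

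- *Different drugs, or a different BP threshold.* A reader might infer either. The active substance, 140/90 mmHg and more than 30 minutes are common to both.
- *A 4-hour primary endpoint contaminated by rescue.* Four hours is the observation period. The 4-hour average is used only to decide on a 100 mg visit after an excessive response to 200 mg. The efficacy window is 60-120 minutes.
- *A shifted Safety #1 proportion.* Where systolic pressure drives the rescue, that event has normally occurred already.
- *A rescue rate read from the plan's other figures.* Hypothesis 1.2 (under 10%) uses 140/100 mmHg and includes intolerable side effects. The 7 of 21 hypertensive responses were on midodrine. Neither is a rescue rate. The plan's own droxidopa data at 400 mg in 10 subjects show three people with one reading each of 140 mmHg or more, 3% of recordings. These are single readings, at half the 800 mg maximum planned here.

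**Conclusion.** Wrong as written: an internal contradiction in a safety instruction. The documents cannot both be followed on product and route at JJPVAMC and ISMMS. They also differ on which step the 30 minutes starts and on whether a physician's decision is needed, although on timing alone one course of action can satisfy both.

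The safety inconsistency is certain from the text. The statistical consequence is only a possibility: rescue before 120 minutes could alter the average that defines a normotensive response. Its frequency is not stated and is probably low, given the early and sustained elevation it requires. That judgement assumes 15-minute readings and no drug before more than 30 minutes of elevation. A reader should not infer that the primary proportions will differ by document. No view is taken here on which product or rule is clinically right.

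**What to change.** Reconcile Laboratory Monitoring in the Protocol with item 15e of the combined document so that one product and route, one trigger and one decision step appear in both and in the instructions at every site, KF included. Which ones is for the sponsor and the study physician to decide.

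Add fields to the case report form for the agent and the time given, so that readings after rescue can be identified when the 60-120 minute average is computed.

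The cost is a document amendment with a small form change; no extra visits or staff are needed.

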PART II

A Research Protocol must be submitted with this application.

A. LAY RESEARCH SUMMARY

Provide 1-2 paragraphs explaining the Research in lay terms, including the specific study aim, any important background information to explain why the research is important, what will be done, and how results will be analyzed.

The goal of this study is to determine the efficacy of the drug Droxidopa (Northera) in increasing blood pressure in subject with hypotension, low blood pressure, which is classified as blood pressure less than 110/70 in males and 100/70 in females. The first aim is to determine the proportion of subject with SCI who have a normotensive response to Droxidopa. The second is to determine the proportion of subject with SCHI who express a hypertensive response to Droxidopa. A Normal blood pressure ranges from 111-139 in males and 101-139 in females and a hypertensive blood pressure is anything higher than 140 in males and females.

The study would take place in James J. Peters VA Medical Center (JJPVAMC), The Icahn School of Medicine at Mount Sinai (ISMMS) in Manhattan, New York and The Kessler Foundation (KF) at the Kessler Institute for Rehabilitation in West Orange, NJ.

B. PROTOCOL SUMMARY

A. Provide a brief (200-250 word) summary of background information for physician/scientistsList total # of subjects approved for enrollment by the IRB.
List total number of subjects enrolled (Signed a consent form) over the life of this study. List total number of subjects enrolled(Signed a consent form) in the current approval period. List total number of subjects terminated from study (Lost to follow-up, terminated by PI, withdrew consent, etc.). List total number of subjects that have completed all study tasks/procedures and follow-up visits. List total number of subjects currently receiving study treatment or participating in study activities.:

Interruption of sympathetic cardiovascular autonomic regulation following spinal cord injury (SCI) is associated with significantly reduced plasma norepinephrine (NE) levels, hypotension and orthostatic hypotension (OH), particularly in individuals with high cord lesions. [1-4] Although the incidence of hypotension is reported to be as high as 70% in persons with cervical lesions (i.e., tetraplegia), the vast majority of these individuals remains asymptomatic and, therefore, does not raise clinical concern, or prompt intervention [5, 6]. While it is appreciated that clinicians are faced with substantial challenges in managing blood pressure (BP) in persons with SCI, contrary to the prevailing belief, asymptomatic hypotension and OH are not benign conditions. Reports suggest that asymptomatic hypotensive individuals with SCI may have subclinical cognitive dysfunction affecting memory and attention processing [7-11] and increased incidence of fatigue and depression compared to normotensive individuals with SCI. [7] It must be appreciated that to date, there are no FDA approved pharmaceutical options proven to be safe and effective for treatment of hypotension and OH in the SCI population. Until 2014, midodrine hydrochloride was the only agent with FDA approval for treatment of symptomatic neurogenic OH (NOH). Midodrine, an alpha-agonist, is the most commonly prescribed agent used to treat symptomatic hypotension in the SCI population despite a lack of convincing evidence of safety or efficacy. [12] In 2014 droxidopa (L-threo-3,4-dihydroxyphenylserine - NORTHERA; Chelsea Therapeutics, Charlotte, NC) was approved by the FDA for treatment of symptomatic NOH based on data collected in conditions of autonomic dysfunction. Droxidopa is a NE precursor that is stored in neuronal and non-neuronal tissue and has been shown to increase standing BP and reduce symptoms of orthostatic intolerance in individuals with symptomatic NOH. [13-15] We recently reported preliminary evidence of a mean increase in seated BP in individuals with SCI following oral administration of 400 mg of droxidopa; however, this dose was effective in only 5 of the 10 subjects tested and the BP effect waned over a 4-hour observation. [16] Because of its unique pharmacokinetic profile, [17] droxidopa is a highly promising agent to treat hypotension in persons with SCI. As such; there exists a pressing imperative to determine the clinical value and safety of droxidopa in hypotensive individuals with SCI.

B. State the purpose of the study:

Primary Aim 1.1: Dose optimization, open-label trial to determine the proportion of subjects with SCI with a normotensive response to droxidopa (Efficacy #1). Normotension will be defined as an average systolic BP (SBP) recorded 60-120 minutes after dose administration of 111-139 mmHg in males and 101-139 mmHg in females or a maximum dose of 800 mg is reached without adequate SBP response.

Primary Aim 1.2: Dose optimization, open-label trial to determine the proportion of subjects with SCI with a hypertensive response to droxidopa (Safety #1). Hypertension will be defined as a sustained elevation (≥ 30 consecutive minutes)

in seated SBP \geq 140/100 mmHg or intolerable side effects considered related to study medication.

Secondary Aims: To determine the effect of the individualized optimal dose of droxidopa, compared to placebo, on (1) supine BP (Safety #2), (2) SBP during a head-up tilt (HUT) maneuver to 70° (Efficacy #2) and change in cerebral blood flow velocity (CBFv) from supine to HUT (Efficacy #3).

C. Background of Study Population - Clinical Information:

- a. Describe the general population from which you plan to recruit subjects for this study (i.e., Demographics of potential subjects):

All eligible participants, including women and minorities, will be included in this investigation if they demonstrate an understanding of the study procedures, meet entrance criteria, and sign the informed consent. Individuals will be recruited from prior study participation and referral from primary physicians.

- b. Describe the medical condition in this population:

Subjects have experienced a spinal cord injury, experienced muscle paralysis below the level of injury, and have a variety of secondary medical consequences such as cardiovascular disease, pressure ulcers, osteoporosis, and diabetes. In addition, it is not uncommon for them to have received an initial dual diagnosis of traumatic brain injury and SCI.

- c. How does this condition affect this population (symptoms)? Depending on the level of injury subjects may have blood pressure dysregulation, elevated resting heart rate, reduced blood flow to the brain, and impaired cognitive function in addition to decreased levels of upper and/or lower body sensory and motor function.

- d. Does this population have an understanding or knowledge of the medical condition being studied? Many of the subjects who have been injured longer do have an understanding of their injury and the problems associated with it. Subjects who are acutely injured may not have been provided with a vast amount of knowledge on their injury but they will not be recruited for this study.

- e. What is the traditional treatment provided for this condition?

Traditional treatments address the secondary medical consequences of SCI via prevention and specific organ system therapies. Some individuals undergo experimental therapies in an effort to regain function.

- f. Explain how special needs that may arise with this population due to this medical condition are addressed (e.g. Additional care provided, supportive therapy, physiotherapy, behavioral therapy):

We accommodate subjects as best as possible by providing physical assistance for transferring, preparing for the study, and completing study-related paperwork. In addition, all our resources (i.e., bathroom, desks and doors) are wheelchair accessible.

- g. Describe how research subjects will be referred for appropriate care while they are enrolled in the study? **If, and when necessary, all participants will be referred to the appropriate clinical personnel given the medical concern presented.**
- h. Describe whether providers (all clinical staff) have experience in providing care to subjects: **There are several physicians at the site that have been board certified for a number of years and have excellent experience.**
- i. Does the James J. Peters VAMC have the appropriate medical or psychosocial resources required for any emergency needs for research subjects? **The JJPVAMC is an SCI center and cares for more than 300 veterans with SCI as both in-patients and outpatients; medical resources are available if emergently required.**

4. Selection of subjects:

- a. Indicate number of subjects to be enrolled at this site (**Total # of subjects approved by IRB**):

A total of 75 subjects will be screened (25 at JJPVAMC; 25 at ISMMS; 25 at KF). Of those 75 screened, 60 eligible subjects will be enrolled for study 1 (20 at JJPVAM; 20 at ISMMS; 20 at KF). From those 60 who complete study 1, A total of 30 will be enrolled for study 2 between all sites.

- b. Indicate total number of subjects to be enrolled, if multisite study:

A total of 75 subjects will be screened. (25 at JJPVAMC; 25 at ISMMS; 25 at KF)

A total of 60 subjects will be enrolled for study 1. (20 at JJPVAM; 20 at ISMMS; 20 at KF)

A total of 30 subjects will be enrolled for study 2. (between KF, ISMMS and JJPVAMC)

- c. Are veterans being enrolled at this site?

YES	X	NO	
------------	----------	-----------	--

- d. Are non-veterans being enrolled at this site?

YES	X	NO	
------------	----------	-----------	--

If no, proceed to question 4.f.

Justify why non-veterans will be enrolled at this site: **Non-veterans are being enrolled to meet the study's enrollment number and to broaden the population pool.**

Of all subjects to be enrolled at this site, what percentage will be non-veterans? **This number cannot be determined given the unknown demographics of patients at the site. However it is likely that a greater percentage will be non-veterans as the ISMMS is not a veteran care institution.**

- e. Describe the setting in which the research will be conducted (e.g., research office, clinic, lab, inpatient unit, outpatient unit):

The study will take place at James J. Peter VA Medical Center in the Spinal Cord Injury Research Department in room 7A-13. All necessary equipment needed for the study is present in that department.

ISMMS: The research will be performed at Mount Sinai School of Medicine in the Klingstein Clinical Center (KCC) building on floor KCC2 in the Rehabilitation in-patient ward. All necessary equipment needed for the study is present in that department.

KF: The research will be performed at Kessler Foundation at the Kessler Institute for Rehabilitation, [name] in the main building, Room L050. All necessary equipment needed for the study is present in that department.

f. What is the expected length of time a study subject will participate? (i.e., number of days, weeks, months, years) **Qualified subjects will come in for 10 visits, including the screening visit for study 1. They will then come in for an addition 2 visits for study 2 if they qualify. The approximate maximum length of time they would be participating in the study would be 11 weeks if they come in once a week.**

5. Indicate the characteristics of study population (with the letter x in the appropriate column):

a. Gender:

	YES	NO
Male	X	
Female	X	

b. Age range: from _____ to _____ [max age is 89 years]

c. Racial and Ethnic/Minority Groups:

	YES	NO
Caucasian	X	
Alaskan Native	X	
American Indian	X	
Hispanic	X	
Black	X	
Asian/Pacific Islander	X	

Other: (Specify)

d. Justify any exclusion of specific gender, age, and racial or ethnic groups:

N/A

6. State inclusion criteria for enrollment in study:

Study 1:

- 1) Male or Female, age 18 to 89 with traumatic SCI.
- 2) SCI Subjects (n=40):
 - a) Any level of injury;
 - b) Any AIS grade of SCI;

- c) Non-ventilator dependent
- d) Primarily wheelchair dependent for mobility;
- e) Duration of injury < 1 year

3) Low Blood Pressure:

Systolic BP less than 110 mmHg and/or diastolic BP less than 70 mmHg for males;
Systolic BP less than 100 mmHg and/or diastolic BP less than 70 mmHg for females;

4) Primary Language is English.

Able to provide informed consent

Study 2:

5) Male or Female, age 18 to 89 with traumatic SCI.

6) SCI Subjects (n=40):

- a) Any level of injury;
- b) Any AIS grade of SCI;
- c) Non-ventilator dependent
- d) Primarily wheelchair dependent for mobility;
- e) Duration of injury < 1 year

7) Low Blood Pressure:

Systolic BP less than 110 mmHg and/or diastolic BP less than 70 mmHg for males;
Systolic BP less than 100 mmHg and/or diastolic BP less than 70 mmHg for females;

8) Primary Language is English.

Able to provide informed consent

9) Showed a normotensive blood pressure in response to Droxidopa during study 1.

7. State exclusion criteria for enrollment in study:

Study 1 and Study 2:

- Current illness or infection
- Individuals with frequent or severe autonomic dysreflexia
 - a. More than 3 symptomatic events per week
 - b. BP \geq 140/90 mmHg
 - c. Significant adverse subjective symptoms reporting
- Hypertension
- Any neurological condition other than SCI (Alzheimer's disease, dementia, stroke, multiple sclerosis, Parkinson's disease, etc.)
- History of epilepsy or other seizure disorder
- History of traumatic brain injury (TBI)
- Liver or kidney disease
- Bladder problems including blockage of the urine and/or weak urine stream.
- Diagnosis of a psychiatric disorder such as schizophrenia or bipolar disorder
- Known artery disease, heart failure, AV block, and irregular heartbeat
- Any allergies to droxidopa, aspirin, polyethylene oxide, polyethylene glycol, hydroxypropyl cellulose, butylated hydroxytoluene, magnesium stearate, hypromellose, yellow ferric oxide, and red ferric oxide
- Major surgery in the last 30 days
- Illicit drug abuse in the past 6 months
- Pregnant
- Your prescription medications will be reviewed by the study investigators and research staff.
If you are currently taking medications to treat any of the following please make the investigators aware:

- d. Depression, Schizophrenia, ADHA
- e. Pain (opioids)
- f. Infection or illness (antibiotics)
- g. Erectile dysfunction (Viagra, Cialis, etc.)
- h. Overactive bladder
- i. High or low blood pressure
- j. Migraine headaches
- k. Malaria
- l. Ashtma

8. Will vulnerable subjects be enrolled in this study?

YES	NO	
------------	-----------	--

	YES	NO
Individuals with lack of decision-making mental capacity		X
Economically/socially disadvantaged persons	X	
Educationally disadvantaged persons	X	
Pregnant women, for minimal risk only		X

Fetuses Requires Medical Center Director authorization. See IRB SOP.

Children Requires Medical Center Director authorization. See IRB SOP.

Prisoners Requires CRADO authorization. See IRB SOP.

If Yes for any answer, provide a means by which vulnerability is determined: **We will not be determining vulnerability; however, it is possible that an economically or socially disadvantaged individual may consent to participate in this study.**

9. Are prospective subjects likely to feel vulnerable to coercion or undue influence to enter the study?

YES	NO	X
------------	-----------	----------

a. Are there any payments to subjects?

YES	X	NO	
------------	----------	-----------	--

b. If No, proceed to question 9.c.

How much are the payments? **\$25 for the screening session and \$50 for the testing sessions for study 1 and study 2**

Provide a schedule (timing) of payments.

Study 1- up to \$425.00

Visit 1 (1 hours)-\$25.00

Visit 2 (5 hours)-\$50.00

Visit 3 (5 hours)-\$50.00
Visit 4 (5 hours)-\$50.00
Visit 5 (5 hours)-\$50.00
Visit 6 (5 hours)-\$50.00
Visit 7 (5 hours)-\$50.00
Visit 8 (5 hours)-\$50.00
Visit 9 (5 hours)-\$50.00

Study 2- up to \$100.00

Visit 10 (5 hours)-\$50.00
Visit 11 (5 hours)-\$50.00

In your opinion, will such payments have any influence on a person's decision to participate?

YES	NO	X
------------	-----------	----------

Why or why not?

The subject stipend that is offered is not coercive and should not have any influence on the subject's decision to participate for the following reasons:

- Payment for participation will not be discussed during the recruitment process unless a question is specifically asked by the participant.
- The stipend offered is as compensation for participants' time and travel; and is reasonable given the duration of testing.

c. What special safety precautions are utilized to minimize risk of coercion to protect the rights and welfare of these subjects [e.g., avoid financial incentives, consult with patient advocates or representatives]? **Participants will be given many opportunities to ask questions and to review the consent with their primary care physicians.**

10. As PI, do you have access to sufficient population that will allow recruitment of the necessary number of subjects?

YES	X	NO
------------	----------	-----------

11. Indicate how potential subjects will be recruited:

Potential participants will be recruited via primary care referral from a KF, ISMMS or JJP VAMC care provider or from prior enrollment in a research study. All subjects will be recruited in accordance with HIPAA and local IRB guidelines by the co-investigator by telephone or on the day of their regularly scheduled appointment.

12. Description of the Consent Process:

- a. Describe the enrollment procedures for participation in the study:
Participants contact or are referred to a Co-investigator at KF, ISMMS and JJP VAMC and will provide information relative to the inclusion criteria. If the participant displays interest in participating, the co-investigator will thoroughly review the consent documents, and after the consent process is complete a testing date is scheduled.

- b. Indicate when and where consent will be obtained:

The informed consent process will be conducted in the privacy of the research laboratory at a time that is convenient for the participant and research staff, prior to initiation of study procedures.

c. Who will conduct the consent interview?

Research staff members associated with the research protocol as listed on the assurance page will conduct the consent interview.

d. Will a legally authorized representative provide consent or permission for a subject, as appropriate?

YES	X	NO	
------------	----------	-----------	--

e. What is the waiting period between informing the prospective subject about the study and obtaining consent?

There is no defined waiting time between completion of the informed consent process and initiating study procedures. However, the informed consent process will be completed prior to initiating study procedures.

Time devoted to consent discussion? The participant will be given adequate time to read the consent and ask questions. As long as necessary.

Time allowed for a decision? Subjects will be reminded that they may take the consent home and review it with their family and/or primary care physician. As long as necessary.

f. How will you insure that the language used by those obtaining consent will not include exculpatory language which would waive or appear to waive any of the subject's legal rights? **The IRB approved consent will be read verbatim to the participant or translator. Participants will be asked to reiterate the study procedures and goals, any uncertainty will be clarified by study team members.**

g. How will you insure that the information being communicated to the subject or the representative during the consent process will not include exculpatory language through which the subject or the legally authorized representative releases or appears to release the investigator, the sponsor, the institution, or its agents from liability for negligence?

The consent form has information on the rights of the participant and the responsibilities of the investigator, the institution and/or its agents toward the participant as a consequence of his/her participation in the study. This consent form will be discussed with the participant in detail, and will clearly state the above-mentioned participant's rights and the investigator's/institution's or its agent's responsibilities in non-exculpatory language. Investigators and coordinators will have completed all mandatory training.

h. How will you know that the language is understandable to the prospective subject or the legally authorized representative?

Eligible participants will be given a copy of the consent to read through at home at their own leisure. After about one (1) week the investigator, or a representative, will call the participant to go over the details of the consent and ask if there are any questions prior to scheduling a study visit. Before signing the consent, potential participants or their surrogate will be asked to concisely reiterate what they understand about the study, its objectives, and the consent form in their own words in a clear, concise and accurate manner. Only after the investigator/representative has received signed informed consent, will studies be performed with any subject.

i. Indicate how you will determine whether the subjects (or their surrogates) understand the content of the information that is provided in the consent document:

Through open dialog with the study participant or his/her surrogate the investigator/representative will gain an understanding of the potential participant's ability to objectively discern the study procedures and his/her role in participating. The coordinator will emphasize the voluntary nature of participation in the study. Participants or their surrogate will be asked to reiterate what they understand the implications of their decision to, or not to, participate in the study are. If the participants or their surrogate demonstrate inability to communicate a decision, they will not be enrolled in the study and the consent process will cease.

j. How will you insure that the consent process will minimize the possibility of coercion or undue influence?

The relationship between study investigators and study participants is and will remain exclusively for the purposes of research. We maintain open dialog with the study participant or his/her surrogate at all times and as such we have an understanding of the potential subject's ability to objectively discern the study procedures and his/her role in participating. Reimbursement is allocated for the time investment in the research process for study participants and is not excessive. Participants will be afforded the opportunity to ask as many questions as they desire, speak to other individuals regarding their participation and schedule testing at their leisure.

13. Summarize what actually will be done to the subjects during their participation in the study:

a. Provide a clear description of what is being done for research purposes and what is being done as part of "usual care":

All procedures are being performed for research purposes.

b. Provide a detailed **list of tests and procedures** that will be performed for research purposes (e.g., blood tests, urine tests, cultures, interviews, questionnaires, surgical procedures, cardiac catheterization, pulmonary function tests, X-rays, scans, etc) during the course of the study. **List must indicate tests and procedures only for subjects who sign a VA consent form, regardless of where tests and procedures take place:**

Test /Procedure:	Where:	Performed by Whom: (Insert Name or TBD if not yet known)	When:	# of times:
Heart Rate and Breathing Rate	KF:L050/JJP VAMC: 7A13/ISMMS: KCC2	[name] [name] [name] [name] [name] [name]	All visits	Continuous
Brachial Blood Pressure	KF:L050/JJP VAMC: 7A13/ ISMMS: KCC2	[name] [name] [name] [name] [name] [name]	All visits	1x/minute
Finger Blood Pressure	KF:L050/JJP VAMC: 7A13/ ISMMS: KCC2	[name] [name] [name] [name] [name] [name]	All visits	Continuous
Cerebral Blood Flow	KF:L050/JJP VAMC: 7A13/ ISMMS: KCC2	[name] [name] [name] [name] [name] [name]	2 visits	Continuous
Orthostatic Hypotension (OH) questionnaire	KF:L050/JJP VAMC: 7A13/ ISMMS: KCC2	[name] [name] [name] [name] [name] [name]	All visits	Continuous
Fatigue Survey	KF:L050/JJP VAMC: 7A13/ ISMMS: KCC2	[name] [name] [name] [name] [name] [name]	All visits	2x/visit
Head-Up Tilt (HUT)	KF:L050/JJP VAMC: 7A13/ ISMMS: KCC2	[name] [name] [name] [name] [name] [name]	2 visits	1x/visit
Plasma catecholamine collection (20mL)	KF:L050/JJP VAMC: 7A13/ ISMMS: KCC2	[name] [name] [name] [name]	2 visits	4x/visit

c. If laboratory tests are part of this protocol, will some or all study-related tests be performed outside this medical center?

YES	NO	N/A	X
-----	----	-----	---

d. Provide a statement that defines who will be financially responsible for the costs associated with participation in the study (e.g., examinations, procedures, drugs, devices, etc.) and a statement that defines what will be provided without cost to the subjects:

Funds from the New York SCIRB program (Grant # DOH01-PART2-2017-00043) will be used for all expenses associated with the study (see attached Budget).

e. VHA Health Record (If yes to (i) below or if clinical resources are to be used, a VHA health record must be created in CPRS [VHA Handbook 1200.05 #29j].

(i) Will the research intervention possibly lead to physical or psychological adverse events?

YES	X	NO	
-----	---	----	--

(ii) Do you have a process in place to include a copy of the signed informed consent and HIPAA authorization in the medical record for the type research described above for each subject?

YES	X	NO	
-----	---	----	--

